The proposed study will be conducted in kindergartens in Hong Kong. The communal water supply in Hong Kong is fluoridated at a concentration of 0.5 ppm. Most child formula toothpastes available in Hong Kong contain fluoride at a concentration of 500–600 ppm. Generally healthy children aged between 3-4 years with no remarkable medical history will be invited to participate in this study. Children with at least one of the following criteria, deemed to be at moderate to high caries risk (American Academy of Paediatric Dentistry, 2013), will be included in this study:

Moderate risk	The child is a recent immigrant.
	The child has plaque on teeth.
High risk	The parent/ caregiver has low socioeconomic status.
	The child has >3 between meal sugar-containing snacks or beverages per day.
	The child is put to bed with a bottle containing natural or added sugar.
	The child has >1 decayed/missing/filled

	surfaces.
	The child has white spot lesions or enamel defects.
	The child has visible cavities or fillings.

They are thus qualified to receive fissure sealants and topical fluoride application regularly every 3 months (Lee, 2015; AAPD, 2013).

The following will be excluded from this study:

1. Children with the presence of caries of ICDAS code 3, 4, 5, or 6 on other primary teeth.
2. Children who had received professional fluoride application in the past 6 months.
3. Children with serious systemic disease or taking long term medication.
4. Children who are uncooperative or refuse the treatment.
5. Second primary molars that are (i) with caries in dentin indicated by ICDAS code 4, 5 or 6; (ii) partially erupted; (iii) with fillings and/or sealants; and (iv) hypoplastic or hypomineralized.

(ii) Methods

Sample size calculation

The primary outcome of this clinical trial is carious cavity development into dentin (ICDAS code 4,5 and 6) on occlusal surfaces of primary second molars. Sample size is calculated to be 256 children with a type I error of 0.05 and a power of 90%. This is based on the results of a previous study on primary molars (Honkala et al., 2015), where the real difference between fluoride varnish and sealant effect on occlusal caries reduction was 30%. Calculating with a 5% statistical significance level and a 90% power, a minimum of 102 children in each group will be required. To allow for loss of power due to drop-out, the initial sample size should be around 25%

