4	Underlying dark shadow from dentin with or without localized enamel breakdown	The carious lesion appeared like a shadow of discolored dentin appeared through an apparently intact enamel, which might show signs of localized breakdown.
5	Distinct cavity with visible dentin	Cavitation in opaque or discolored enamel exposing the dentin beneath, involving less than half of the tooth

		surface.
6	Extensive distinct cavity with visible dentin	Cavitation in opaque or discolored enamel exposing the dentin beneath, involving at least half of the tooth surface. Obvious loss of tooth structure and dentin is clearly visible on the walls and at the base in a cavity that involved at least half of the tooth surface.

Questionnaire survey

Parents are required to complete a validated questionnaire before the baseline examination, which consists of the following sections:

- (1) The child's personal information - gender, age, place of birth, medical history of systemic disease and long term medication
- (2) The child's oral health-related behaviors – snacking habit, frequency of toothbrushing, parent's supervision in toothbrushing, use of toothpaste and night bottle habit
- (3) The child's dental history – past dental treatment received
- (4) The child's socio-economic background - parents' age, education level, household income and number of children

(iii) Study design

Clinical exam

Clinical examination will be carried with the child lying supine on table provided by the kindergarten.

The Visible Plaque Index (VPI) (Ainamo & Bay, 1975) will be used to measure the oral hygiene status of the child. Buccal and palatal/lingual surfaces of 6 index teeth (teeth 55, 51, 63, 71, 75, 83) will be examined. The presence or absence of visible plaque on the tooth surfaces mentioned above will be recorded as "1" or "0" respectively. The VPI score of the child will be obtained by dividing the number of

tooth surfaces recorded as “1” with the total number of tooth surfaces recorded as “0” and “1”, i.e.

$$\text{VPI} = \frac{\text{number of tooth surfaces recorded as “1”}}{\text{total number of tooth surfaces recorded as “0” and “1”}}$$

b. Tooth status

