For the sealant group, glass ionomer sealants will be applied using the finger pressure technique described in the WHO manual for atraumatic restorative treatment (ART) (Frencken et al.; 1997). The primary second molars included in the study will first be cleaned and dried by wiping with gauze and cotton pellets. Following the manufacturer's instructions, further cleaning of the fissures will be performed by applying GC cavity conditioner with micro-applicator for 10-15 seconds, then clean with wet cotton pellets for several times. The surface will be dried with cotton pellets. The dental assistant will mix the glass ionomer sealants (GC Fuji VII) in a standardized proportion with an amalgamator. Glass ionomer sealants will be applied to the occlusal surface with blunt end of an applier and slightly overfilled. A gloved finger with petroleum jelly will be used to push and rub the materials into the pits and fissures, as well as removing the excess sealants from the tooth surfaces. The sealants will be covered and protected by a layer of petroleum jelly (Vaseline®).

In the NaF varnish groups, 0.25mL (one drop) of the varnish will be placed in a plastic dappen dish. A disposable microbrush will be used to apply the varnish onto the second primary molars included in the study and all other teeth. The child will be instructed not to eat or drink after the application of varnish for at least half an hour.

Follow-up evaluation

Children in the NaF varnish group will be recalled at the 3rd, 6th, 9th, 12th, 15th, 18th, 21st and 24th months for reapplication of fluoride varnish. Similar to baseline, 0.25mL (one drop) of the 5% sodium fluoride varnish will be applied using a disposable microbrush. At the 6th, 12th, 18th and 24th months, a clinical examination will be performed for all children in both groups. During the follow-up examination, overall VPI and dmft will be recorded. ICDAS score will be recorded for each primary second molar included in the study.

Sites with sealant will be evaluated in the following aspects:

Aspect	Code	Classification	Description
Retention	0	Fully intact	Sealants are fully intact without apparent loss of materials.
	1	Partial loss	Sealants are retained with partial loss
	2	Total loss	No sealant materials are found on tooth surface.
Caries	0	No caries	No caries found at the margin of the sealants.
	1	Presence of caries	Evidence of caries found at the margin of the restoration.

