A 10% random sample will be re-examined during every examination to monitor intra-examiner reproducibility.

An oral health talk will be given to the parents of the participants. During the talk, the parents will be instructed to choose fluoridated toothpastes and child toothbrushes throughout the period of study. In case of any adverse event during the study, the parents will be advised to contact the principal investigator.

Outcome measures

The primary outcome measure is carious cavity development into dentin (ICDAS code 4, 5 and 6) on the occlusal surfaces of primary second molars over time.

Only one registered dentist will be the examiner in the kindergarten throughout the whole 24-month study period. She will receive training and calibration by epidemiologists before examining the subjects. The following dental equipment will be used:

- (1) Disposable dental mirror attached to a handle with light-emitting diode intra-oral illumination
- (2) World Health Organization CPI periodontal probe(405/WHO probe)

A 10% random sample will be re-examined during every examination to monitor intra-examiner reproducibility. The ICDAS score will be recorded based on the index proposed by Ismail et al., 2007.

Parents will be notified about the development of carious lesions. Advice on oral hygiene maintenance and seeking private dentists for respective dental treatments will be given to the parents in the form of a detailed report.

The proposed study will be a randomized controlled trial with 2 parallel groups. The unit of randomization will be each individual participant, but not each tooth of the mouth.

(iv) Data processing and analysis

Data analysis will be performed using SPSS® Statistics version 23.0 (SPSS Inc, Chicago, IL, USA). All children with missing data resulting from loss to follow-up or unrecorded data will be excluded from the analysis. Data proof-reading will be performed after data entry to identify and correct any errors before analyzing the data. An intention-to-treat analysis will be undertaken. Intra-examiner agreement in the diagnosis of dental caries will be assessed by Cohen's Kappa statistics.

Chi-square test will be used to assess the difference between groups according to the distribution of children's demographic characteristics such as gender, place of birth, oral health-related behavior, use of fluoride toothpaste, snacking habit, parents' education and family income.

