The outcome measures are the mean change in the overall dmft scores and ICDAS code in primary second molars over time. Within-group comparison of changes in mean overall dmft scores and ICDAS scores at 24 months and mean change in overall dmft scores and ICDAS scores will be assessed by applying repeated analysis of variance (ANOVA) (or Friedman test for non-parametric data).

Student's t-test will be applied to differentiate the comparability between the treatment groups according to the subject's baseline conditions, including the child's age, dmft score and VPI score.

Since more than one molar will be included from one child, GLIMMIX procedure will be used to adjust for the clustering effect. The first level and second level will be the primary second molar and the subject

respectively. This analysis accounts for the correlation (clustering) between observations of multiple molars from the same child.

A multi-level logistic regression analysis will be performed to analyze the effects of independent variables on the ICDAS scores at the 6, 12, 18 and 24 month examinations. The independent variables included the child's demographic characteristics, oral health-related behaviors and clinical characteristics (gender, place of birth, frequency of tooth brushing, use of fluoride toothpaste, snacking habits, mother's education, father's education, family income, VPI score, dmft score and the treatment group). The level of statistical significance for all tests will be set 5%.

Key References:

3. American Academy of Pediatric Dentistry. Guideline on caries-risk assessment and management for infants, children, and adolescents. *Pediatr Dent.* 2013;35(5): E157-64.
4. American Dental Association Council on Scientific Affairs. Professionally applied topical fluoride: evidence-based clinical recommendations. *J Am Dent Assoc.* 2006;137(8): 1151-9.

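### The analysis called intention-to-treat would be a complete-case analysis, with no sensitivity analysis to show what the excluded children could change

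*Combined protocol and SAP*

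**What the plan says.** Two statements stand close together in section d)(iv), Data processing and analysis. The first is a rule: "All children with missing data resulting from loss to follow-up or unrecorded data will be excluded from the analysis". Two sentences later comes a principle: "An intention-to-treat analysis will be undertaken". No analysis set is defined, and nothing explains how the two fit together.

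The primary outcome, under Outcome measures, is "carious cavity development into dentin (ICDAS code 4, 5 and 6) on the occlusal surfaces of primary second molars over time". Follow-up evaluation gives four occasions on which it can be missed: "At the 6th, 12th, 18th and 24th months, a clinical examination will be performed for all children in both groups".

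Later in d)(iv) a mixed-model procedure is planned, for one stated reason: several molars come from the same child. A multi-level logistic regression will then study the "effects of independent variables on the ICDAS scores at the 6, 12, 18 and 24 month examinations". Its covariates cover "oral health-related behaviors and clinical characteristics (gender, place of birth, frequency of tooth brushing" and further items, eight of which come from the parents. Under Questionnaire survey, "Parents are required to complete a validated questionnaire before the baseline examination".

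Under Sample size calculation, "a minimum of 102 children in each group will be required". This is raised by about a quarter to 128 per group, and the reason given is power lost through drop-out.

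**The concern.** The exclusion acts before any model is fitted. A mixed model could use a child's partial record, but under this rule the child has already been removed. The result would be labelled intention-to-treat although some randomised children, and some recorded outcomes, are not in it.

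The rule can be read in two ways:

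- **Literal.** Any missed examination removes the child altogether, even if ICDAS 4-6 had already been recorded.
- **Visit by visit.** The regression refers to each examination, so the child might be left out only where an examination was missed. An event seen at month 12 still counts at month 12, but it is absent from month 24 if that examination is missed.

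The reference to unrecorded data adds a third route. A child with complete dental records could be dropped because one questionnaire item is blank. The requirement that parents complete the questionnaire makes this less likely but does not exclude it.

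At stake is whether a reader can tell how far the primary comparison depends on the children left out. As planned, no analysis would show this.

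**Working it through.** **From the documents**

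The plan's own inflation reproduces: 102 × 1.25 = 127.5, rounded up to 128 per group, or 256 in all.

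If the allowance is used in full, 128 − 102 = 26 children per arm are not analysed. That is 26/128 = 52/256 = 20.3%. With 26 outcomes unknown, the 24-month risk among all children randomised to an arm is bounded only within an interval 20.3 percentage points wide. The worst-to-best-case interval for the risk difference is 2 × 26/128 = 40.6 points wide.

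**Illustrations (every input below is assumed; the documents give none)**

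*Children excluded under the literal reading.* With independent misses at rate d per examination, the share excluded is 1 − (1 − d)^4.

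| d | excluded | left of 128 | required |
|---|---|---|---|
| 5% | 1 − 0.95^4 = 18.5% | 104 | 102 |
| 10% | 1 − 0.90^4 = 34.4% | 84 | 102 |

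*Recorded events affected.* Assume a 40% child-level risk over 24 months with a constant 6-month risk h = 1 − 0.6^(1/4) = 0.1199, and intermittent random misses. The share of children with a recorded event is Σ h(1 − h)^(k−1)(1 − d^(5−k)) over k = 1 to 4. The share with an event and all four examinations is 0.4(1 − d)^4.

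- d = 5%: 0.3957 × 128 = 50.6 recorded, 0.3258 × 128 = 41.7 kept. About 9 of 51 are dropped per arm.
- d = 10%: 0.3908 × 128 = 50.0 recorded, 0.2624 × 128 = 33.6 kept. About 16 of 50 are dropped per arm.

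Under the visit-by-visit reading with the same inputs, about 2 or 4 such children per arm are absent from month 24. Because these misses are random, events go in about the same proportion as children (9/51 = 17.6% against 18.5%). This is lost precision, not bias.

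*Blank questionnaire items.* With 1% blank on each of eight items, between 1.0% (always the same children) and 1 − 0.99^8 = 7.7% (independent blanks) would be dropped.

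*Outcome-related loss, equal in both arms.* True risks are 28% and 40%; 35% of children with an event and 15% of the others are lost.

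- First arm: 0.28 × 0.65 / (0.28 × 0.65 + 0.72 × 0.85) = 0.182/0.794 = 22.9%.
- Second arm: 0.40 × 0.65 / (0.40 × 0.65 + 0.60 × 0.85) = 0.260/0.770 = 33.8%.
- Odds ratio: (0.28/0.72)/(0.40/0.60) = 0.58 in truth; (0.182/0.612)/(0.260/0.510) = 0.58 in complete cases.

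The odds ratio is unchanged and both risks are understated.

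*Outcome-related loss in one arm only.* The true risk is 40% in both arms. The sealant arm loses 35% of children with an event and 15% of the others, which is 0.40 × 0.35 + 0.60 × 0.15 = 23% overall. The varnish arm loses 23% at random. Complete cases show 33.8% against 40%, and the odds ratio is (0.260/0.510)/(0.40/0.60) = 0.76 when there is no effect. Total drop-out is the same in both arms, so a count of losses would not reveal it.

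**The case against.** The best defence is that intention-to-treat is often used to mean no more than analysed as randomised. On that meaning the two sentences can stand together as an as-randomised complete-case analysis. That much is right, and a reader who infers an outright contradiction goes further than the text. But the plan does not say that this is its meaning, and on that meaning the set is still complete cases with nothing to test it.

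A reader might also infer that the treatment effect will be biased. The documents do not support this. They give no expected pattern of loss. Children in the varnish group are recalled eight times and sealant children are seen only at the four examinations. Parents in both groups are told of new lesions and advised to see private dentists. These features make differential or outcome-related loss conceivable, but they do not establish it. The equal-loss example above leaves the odds ratio where it was, and the odds ratio of 0.76 under no effect comes from a scenario chosen to show the mechanism.

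The objection that most of the figures rest on assumed inputs is also fair. Only the 20.3% comes from the documents, and only if the allowance is used in full.

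Two other defences fail. The sample-size inflation is stated to protect power and does nothing about who is missing. The mixed model is planned for clustering, and the exclusion rule removes incomplete records before it can use them.

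**Conclusion.** The point holds and should be fixed. The plan prescribes a complete-case set under an intention-to-treat label and provides no alternative handling of missing data and no sensitivity analysis.

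On the plan's own allowance, up to 26 of 128 children per arm (20.3%) would be left out. How many recorded events go with them depends on which reading of the rule is meant and on visit attendance, neither of which the documents settle.

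Bias in the treatment contrast requires outcome-related loss that differs by arm; that is possible but not shown. Without it, the consequence is lost precision and, if loss is related to outcome, absolute risks that are misstated in both arms.

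A reader might conclude that the planned model has to give way to a time-to-event analysis. It does not: that change is optional, and the planned multi-level logistic model is adequate once it is allowed to use the recorded data.

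**What to change.** - Delete the exclusion sentence. Define the primary set as all randomised children, analysed in their allocated group.
- Let the planned multi-level logistic model (molar within child) use every recorded 6, 12, 18 and 24 month examination, with terms for visit and treatment. A molar then contributes up to four records, so the model should also allow for repeated examinations of the same molar.
- Do not drop a child from the primary treatment comparison for a blank questionnaire item. Fit that comparison without those covariates, or impute them.
- Prespecify one sensitivity analysis: multiple imputation with a tipping point. It should cover all missing outcomes, meaning later drop-outs as well as children with no follow-up examination. The latter contribute nothing to the primary model and enter only here, and the plan should say so.
- Keep the complete-case analysis as secondary, and report missingness by arm and visit.

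The cost is a rewritten paragraph and modest extra analysis work, with no added children or visits. The primary model will rest on a missing-at-random assumption, and the sensitivity analysis is there to test how much the result depends on it.

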fissure sealants are significantly more effective than topical fluoride varnishes in preventing occlusal caries in permanent molars (Levy, 2012; Liu et al., 2012). However, a recent Cochrane review suggested that there was still insufficient evidence to determine superiority of resin or glass ionomer fissure sealants over topical fluoride varnishes for occlusal caries prevention, due to the lack of reliable results and low quality of evidence (Ahovuo-Saloranta et al., 2016).

Also, most studies were conducted on permanent first molars among school children (Ahovuo-Saloranta et al., 2016), whom cooperation and moisture control can be easily achieved. However, application of fissure sealants, especially resin-based sealant, in very young children can be a technique-sensitive procedure. Compared with a mean treatment time of less than 3 minutes for varnish application, application of resin-based sealants required over 15 minutes (Splieth et al., 2001). Moisture control is also of paramount importance for the retention and success of resin-based sealants (Gooch et al., 2009), which may be difficult among young preschool children.

Glass-ionomer sealants can chemically bond to enamel and are more tolerable to inadequate moisture control (Antonson et al., 2012). As its application requires less clinical steps, glass-ionomer sealant is comparatively more acceptable to younger patients and can be used in outreach settings with a large number of participants. The fluoride releasing ability is also beneficial in preventing caries especially at adjacent tooth surfaces (Cagetti et al., 2014). However, its retention rate is significantly lower than that of resin-based sealants (Antonson et al., 2012), its success rate in preventing fissure caries in very young patients is still unknown.

c) Aims and Hypotheses to be Tested:

Aims

To compare the efficacy of glass ionomer fissure sealant versus topical application of 5% sodium fluoride varnish in prevention of occlusal caries among preschool children.

Hypotheses to be tested

Greater reduction in occlusal caries in preschool children by glass ionomer fissure sealant compared to topical application of 5% sodium fluoride varnish.

d) Plan of Investigation:

(i) Subjects

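### The analysis section does not tie its treatment model to the declared primary outcome (occlusal ICDAS 4–6), or to one visit or one overall effect

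*Combined protocol and SAP*

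**What the plan says.** Section c) states a between-group hypothesis: "Greater reduction in occlusal caries in preschool children by glass ionomer fissure sealant compared to topical application of 5% sodium fluoride varnish". Under Outcome measures, the primary outcome is "carious cavity development into dentin (ICDAS code 4, 5 and 6) on the occlusal surfaces of primary second molars over time". The sample size paragraph in d)(ii) names the same outcome with the same cut-off.

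Section d)(iv) reads differently: "The outcome measures are the mean change in the overall dmft scores and ICDAS code in primary second molars over time". It then plans a "Within-group comparison of changes in mean overall dmft scores and ICDAS scores at 24 months", and the sentence continues "and mean change in overall dmft scores and ICDAS scores will be assessed by applying repeated analysis of variance", with a Friedman test as the non-parametric fallback.

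Two further statements in d)(iv) concern modelling. The GLIMMIX procedure handles clustering: "The first level and second level will be the primary second molar and the subject", respectively; no response variable is named for it. A multi-level logistic regression then examines a list of independent variables, treatment group last among them, for their effects "on the ICDAS scores at the 6, 12, 18 and 24 month examinations". All tests use a 5% level.

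Three other statements bear on treated molars. Outcome measures says that parents are told of new lesions and advised to seek private dental treatment. Section d)(iv) excludes children with unrecorded data. The tooth-status table under Recruitment and screening codes a tooth filled for caries without decay as f, a tooth extracted for caries as m, and a tooth with dentin caries as d whether or not it is restored.

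**The concern.** A reader who follows d)(iv) as written finds no test identified as the answer to the trial's own hypothesis on its own primary outcome. Mean ICDAS change and whole-mouth dmft measure something other than the development of dentin caries on an included occlusal surface. The one model that contains treatment has a response stated only as ICDAS scores at four examinations. Which visit counts, or whether one effect over all visits is meant, could therefore be settled after four sets of results have been seen.

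A second gap follows from the first. A molar that develops the outcome may be treated before the next examination. Unless the plan says how such a molar enters the primary analysis, the exclusion rule for unrecorded data could remove a child because the outcome occurred.

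**Working it through.** **1. The stated outcomes side by side**

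| Place | Outcome | Unit |
|---|---|---|
| d)(ii) Sample size; Outcome measures | New occlusal ICDAS 4–6 (primary) | Included second molar |
| d)(iv) | Mean change in ICDAS code | Second molar |
| d)(iv) | Mean change in overall dmft | Whole mouth |

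These can disagree. The exclusion criteria remove second molars coded 4–6, so included molars start at codes 0–3. Take four molars starting at 0. If all move to code 2, mean change is (4 × 2)/4 = 2 with no primary event. If two move to code 4 and two stay at 0, mean change is (2 × 4)/4 = 2 with two primary events. Overall dmft differs further: varnish goes on all teeth and sealant only on the included second molars (Randomization and treatment allocation), so dmft and the occlusal outcome could favour different arms.

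**2. Which planned test addresses the hypothesis**

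- Within-group comparison at 24 months: no, because it does not compare the arms.
- Repeated ANOVA on mean change (second half of the same sentence): possibly, if a group factor is intended, but not on ICDAS 4–6. The Friedman fallback has no group factor.
- GLIMMIX: no response named.
- Multi-level logistic model: suitable in form, with treatment included, but the response is not tied to codes 4–6, to one visit or to one overall effect.

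**3. What the open choice of visit could cost**

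The plan's own figure is a type I error of 0.05, with 102 children per group after drop-out (102 × 1.25 = 127.5, so 128 per group and 2 × 128 = 256). One pre-specified test keeps to that level.

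Suppose instead that treatment were tested at each of the four visits and any significant visit counted. The plan does not state this rule.

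- Bound for independent tests: 1 − (1 − 0.05)^4 = 1 − 0.8145 = 0.185.
- Four equally correlated normal tests, correlation 0.5, 0.7, 0.9, 0.95: 0.156, 0.131, 0.094, 0.080.
- Null simulation with a random-intercept logistic model (molar within child), 102 children per arm, treatment the only covariate, 4,000 runs per setting. Assumed: 1/2/3/4 included molars per child with probabilities 0.1/0.2/0.2/0.5; child frailty SD 1 or 2 on the logit scale; cumulative incidence as shown, since the documents give no event rates.

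| Assumed incidence at 6/12/18/24 months | Any visit, SD 1 / SD 2 | One test of ever ICDAS 4–6 by 24 months, SD 1 / SD 2 |
|---|---|---|
| 8/15/22/30% | 0.126 / 0.126 | 0.050 / 0.050 |
| 2/6/12/20% | 0.149 / 0.151 | 0.055 / 0.052 |
| 10/14/17/20% | 0.109 / 0.097 | 0.052 / 0.047 |
| 20/25/28/30% | 0.094 / 0.085 | 0.052 / 0.045 |

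A child-clustered score test under the same assumed settings gave 0.081–0.145 for any visit. The illustrative range is therefore about 0.08–0.15. The 0.185 bound is not reached, because results at successive visits on the same molars are correlated.

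**4. Treated molars**

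The documents refer affected children for treatment, exclude children with unrecorded data, and give no rule for an included molar found filled or extracted at a later examination. The dmft code alone cannot supply one: a filled molar with decay on another surface is coded d, which hides the filling, and neither f nor m says which surface was diseased. The documents give no treatment rate, so no size can be attached.

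**The case against.** The strongest reply is that a sensible reader can assemble the primary analysis. The cut-off is declared twice, a logistic model needs a categorical response, and 4–6 is the declared one. Section d)(iv) speaks of outcome measures, not of the primary outcome, so it need not displace the earlier declaration. Two arms allow only one treatment contrast. Much of this stands. A reader might infer that the plan leaves the cut-off or the contrast open, or that it has no between-group analysis at all; the documents do not support either inference. What remains is that no sentence links the model to ICDAS 4–6 or settles the visit or joint effect.

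A reader might also infer that the trial will run at an error rate of 0.185. The plan never says that success at any visit would be claimed. One joint treatment test would avoid the inflation, although the two stated levels, molar and child, include none for repeated visits to the same molar. The simulation also omits ten of the eleven listed covariates.

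On treated molars, development over time most naturally means cumulative occurrence, so the plan should not be read as using 24-month status alone and losing earlier events. The ICDAS table is introduced as a summary of a cited index, so its listing of codes 0–6 does not show that the recording system has no code for a filled or missing tooth. The point that survives is narrower: no analysis rule is given.

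**Conclusion.** The concern holds in this form. The outcomes named in d)(iv) conflict with the declared primary outcome, and following that section literally yields no identified test of it. The gaps are the missing link between the planned logistic model and ICDAS 4–6, and the unstated choice of visit or joint effect. The consequence for type I error is conditional: about 0.08–0.15 instead of 0.05 if any significant visit counted, under assumed event rates, frailty and molars per child. The gap for treated molars is real, but its size cannot be derived from the documents. Both should be settled before results are analysed, because they decide what the trial's main conclusion rests on.

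**What to change.** State one primary analysis in d)(iv): the sealant-versus-varnish odds ratio with 95% confidence interval from the planned two-level logistic model (molar within child), tested once at two-sided 5%. The response is whether an included molar was ever recorded as occlusal ICDAS 4–6 at any examination up to 24 months.

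Add rules for treated molars:

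- A molar with a recorded event keeps it after later treatment, and its child is not excluded as having unrecorded data.
- At each examination, record whether the occlusal surface of an included molar has been restored.
- For a molar first found filled or extracted because of caries, with no earlier occlusal ICDAS 4–6, count occlusal restorations and caries extractions as events. Add a sensitivity analysis that does not count them.

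Label mean ICDAS change, overall dmft, visit-specific results and within-group summaries as secondary, and make the group comparisons between-group.

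The cost is mainly wording and one extra recorded item. Early-visit and dmft results lose confirmatory status. Some extractions may reflect non-occlusal disease, which the sensitivity analysis would help to show.
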